While participating in the study, adverse events will be assessed at Virtual Visit 6 and carbon monoxide levels from In-Person Lab Visit 3. Adverse events will typically be identified during the administration of the Health Changes Questionnaire. Other adverse events may be identified by spontaneous reports from the participant. Withdrawal symptoms are considered an adverse event if the symptom had a significant impact on the participant's daily life, caused a major disruption of functioning, or took any medication for it.

- **Health Changes Questionnaire:** If the participant answers "YES" to Questions 1, 2, or 3 the interviewer should assess for adverse events.
 1. Have you had any negative changes in your physical or mental health since your last virtual visit? If yes, briefly describe.

2. Since your last virtual visit, have you received any form of medical care? If yes, briefly describe.
3. Have you had any changes in medication since your last visit?

Physiological data that will be reviewed:

1. CO level: The 'Adverse Event Form' will be completed if the average of two (or three) consecutive measurements in the same visit is:
 - o CO is greater than 50 ppm if CO at Screening/Baseline Visit is < 20 ppm.
 - o CO is greater than 60 ppm if CO at Screening/Baseline Visit is 20 – 34 ppm.
 - o CO is greater than 70 ppm if CO at Screening/Baseline Visit is 35 – 49 ppm.

For the participant's protection, participants will be withdrawn immediately from the study if any of the following occur:

1. Cardiovascular disease (CVD) event: Typically includes MI (heart attack), PTCA (angioplasty/stenting), bypass surgery, stroke, peripheral vascular disease (arterial blockages in arms or legs leading to procedure or surgery). Less common CVD problems would be new cardiac arrhythmias (e.g., new atrial fibrillation) or new valvular disease (e.g., mitral or aortic regurgitation).
2. DVT/PE (deep vein thrombosis/pulmonary embolism, i.e., blood clots in the venous system).
3. Suicide Attempt: A participant will be withdrawn if they attempt suicide at any time during participation in the study
4. Psychiatric Hospitalization: A participant will be withdrawn if they are hospitalized for psychiatric reasons at any time during participation in the study.

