5. Pregnancy: If a participant indicates they are pregnant at Virtual Visit 6 or In-Person Lab Visit 3, they will be withdrawn from the study, and this event will remain open until delivery. At that time the license medical monitor will contact the participant to ask a few questions about the baby's health and will update the open 'Adverse Event Form'.

The following will be monitored and can lead to the participant being withdrawn by the PI:

1. Expired breath CO >80 ppm
2. Any hospitalization or debilitation in which participation in the study could be detrimental to the recovery process. This will be self-reported by the participant and will be reviewed by the site PI and medical monitor to determine whether continued participation in the study is appropriate.
3. If a participant is behaving in an inappropriate or threatening manner, admits to lying about eligibility criteria, including omitting previous medical diagnoses and medications, is participating in other smoking research studies that could affect the primary outcome measures, does not follow study instructions, etc., then the PI can withdraw them from the study at the PI's discretion.
4. If a participant fails to attend her/his Virtual Visit 1 within the 21-day allowable visit window, they will not be eligible to reschedule the visit or continue participation in the study.

References

http://www.ncbi.nlm.nih.gov/entrez/query.fcgi?cmd=Retrieve&db=PubMed&dopt=Citation&list_uids=10465828
2. Kozlowski, L. T. (2015). Prospects for a nicotine-reduction strategy in the cigarette endgame: Alternative tobacco harm reduction scenarios. *International Journal of Drug Policy*, 26(6), 543-547. doi:10.1016/j.drugpo.2015.02.001
3. Kozlowski, L. T. (2016). Cigarette prohibition and the need for more prior testing of the WHO TobReg's global nicotine-reduction strategy. *Tobacco Control*. doi:10.1136/tobaccocontrol-2016-052995
4. Kozlowski, L. T. (2017). Let actual markets help assess the worth of optional very-low-nicotine cigarettes before deciding on mandatory regulations. *Addiction*, 112(1), 3-5. doi:10.1111/add.13515
5. Shatenstein S. Eliminating nicotine in cigarettes. *Tob Control* 1999;8(1):106; author reply 07-9
http://www.ncbi.nlm.nih.gov/entrez/query.fcgi?cmd=Retrieve&db=PubMed&dopt=Citation&list_uids=10465827

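### No scheduled question covers the five mandatory-withdrawal events between screening and product hand-over at In-Person Lab Visit 2

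*Combined protocol and SAP*

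**What the plan says.** The section Identifying Adverse Events fixes the schedule: "While participating in the study, adverse events will be assessed at Virtual Visit 6 and carbon monoxide levels from In-Person Lab Visit 3". The instrument is the Health Changes Questionnaire, listed once, at Virtual Visit 6. Its first question is "Have you had any negative changes in your physical or mental health since your last virtual visit". The second, on medical care, has the same look-back, and the third asks about medication since the last visit. The section adds: "Other adverse events may be identified by spontaneous reports from the participant".

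It then states, as a protection for participants, that "participants will be withdrawn immediately from the study if any of the following occur", and lists five items: cardiovascular event, DVT/PE, suicide attempt, psychiatric hospitalization and pregnancy. Two of them cover the whole of participation: "A participant will be withdrawn if they attempt suicide at any time during participation in the study", and "A participant will be withdrawn if they are hospitalized for psychiatric reasons at any time during participation in the study". The pregnancy item is tied to named visits: "If a participant indicates they are pregnant at Virtual Visit 6 or In-Person Lab Visit 3, they will be withdrawn from the study".

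A separate list gives grounds on which the PI may withdraw someone. For other hospitalization or debilitation it says: "This will be self-reported by the participant and will be reviewed by the site PI and medical monitor".

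**The concern.** In-Person Lab Visit 2 is the last scheduled contact before seven days of take-home use, so it is the last point at which a mandatory-withdrawal rule can stop dispensing. As written, a participant who has had one of the five events since screening, or who knows she is pregnant, and has not volunteered it, is handed the products and told to use only those.

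The protocol's own risk section makes this relevant. It warns that changes in nicotine use or smoking may worsen mood and psychiatric symptoms. It lists palpitations and raised blood pressure for medicinal nicotine, and it justifies pregnancy testing by the risk to participant and fetus.

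The gap is not closed afterwards. The look-back at Virtual Visit 6 does not reach the earlier period, so rules meant to apply throughout participation have no scheduled trigger there at all. Volunteering an event also costs the participant the completion bonus.

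**Working it through.** The plan states no figure on this point to reproduce. The check sets the visit lists side by side and adds up the visit windows.

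| Contact | Health-related content listed | Bears on the five events? |
|---|---|---|
| Telephone screen | Health status; pregnancy/breastfeeding | Yes, preliminary eligibility |
| Virtual Visit 1 | Brief Medical History Questionnaire; medications | Yes, the last medical history |
| In-Person Lab Visit 1 | COVID screener, temperature, CO, urine pregnancy test | Pregnancy only |
| Virtual Visits 2-5 | None (Timeline Follow Back on tobacco and nicotine use, then the marketplace task) | No |
| In-Person Lab Visit 2 | COVID screener, temperature, CO; then hand-over | Nothing shown |
| Virtual Visit 6 | Health Changes Questionnaire | Yes, but health and medical care only since Virtual Visit 5 |

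**Windows** (from the sections on Virtual Visits 2-5, In-Person Lab Visit 2 and Virtual Visit 6):
- Lab Visit 1 to Virtual Visit 2: 1 to 21 days.
- Virtual Visit 2 to 5: 3 days if consecutive, as intended. The allowance of up to 7 days apart gives 7 if it is the total span, or 3 × 7 = 21 if it applies to each gap.
- Virtual Visit 5 to Lab Visit 2: 0 to 2 days.
- Lab Visit 2 to Virtual Visit 6: 7 days.
- Virtual Visit 1 to Lab Visit 1: no window stated; call it g.

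**Lab Visit 1 to hand-over:**
- Minimum: 1 + 3 + 0 = 4 days.
- Intended schedule, maximum: 21 + 3 + 2 = 26 days.
- Seven-day total span, maximum: 21 + 7 + 2 = 30 days.
- Every window at its limit: 21 + 21 + 2 = 44 days.

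This is the interval for pregnancy. The other four events were last covered at Virtual Visit 1, so their interval is g + 4 to g + 26 days, at most g + 44.

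**First scheduled question on the five events after Lab Visit 1:** 4 + 7 = 11 to 26 + 7 = 33 days, at most 44 + 7 = 51. All of these fall after the use week.

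**Look-back at Virtual Visit 6 for health and medical care:** (0 to 2) + 7 = 7 to 9 days.

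**Period these two questions never cover (Lab Visit 1 to Virtual Visit 5):** 1 + 3 = 4 to 21 + 3 = 24 days, at most 21 + 21 = 42, plus g for the non-pregnancy events.

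**Payment** (Compensation): 30 + 4 × 15 + 20 + 50 = $160. A participant withdrawn at Lab Visit 2 has earned 30 + 60 = $90 and forfeits the $50 bonus, 50/160 = 31% of the total. The remaining $20 is the fee for a Virtual Visit 6 that does not take place.

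**The case against.** The instruction to withdraw immediately governs what staff do once an event is known; it does not promise a detection schedule. Before Lab Visit 2 the study exposure is at most four puffs of each of two cigarettes, so placing adverse event assessment after the exposure week is sensible. Several safeguards already operate:
- Serious medical and psychiatric conditions are excluded at entry.
- Exclusion criterion 5 bars anyone who intends pregnancy during the study or will not use adequate protection, which covers the gap.
- Staff speak with participants at four virtual visits, and spontaneous reports are a named route.
- Field products come from the marketplace without normal-nicotine cigarettes. For a daily smoker, withholding them may simply mean a return to the usual brand.

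The yield would also be small. The documents give no event rates. Assume a combined rate of 1% to 10% per year. Then 100 participants over 26 days give 100 × 26/365 = 7.1 person-years and about 0.07 to 0.7 events; over 44 days, 12.1 person-years and about 0.1 to 1.2. Only events not volunteered would be newly found.

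All of this limits the weight of the point, and the absence of adverse event questions during the purchasing phase is not in itself a fault. What remains is that two of the rules expressly run throughout participation, and that following the plan to the letter would dispense products to someone who meets a mandatory-withdrawal rule.

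A reader might infer that participants have no health check before hand-over. That goes too far: the COVID screener, temperature and CO are all listed at Lab Visit 2. The screener's items are not reproduced, and nothing shows that they cover these events. The consent pages are not in the text and may ask participants to report such events, but that would not be a scheduled question.

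**Conclusion.** The point holds as a cheap improvement. The five mandatory-withdrawal rules have no scheduled trigger before dispensing, and the pregnancy rule as worded names only visits after the use week. The intervals rest on the stated windows and on reading screening as Virtual Visit 1 plus In-Person Lab Visit 1. The 44-day figure needs every window at its limit.

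Two stronger readings are not supported. One is that the gap exposes participants to more harm than their usual smoking: they already smoke daily and choose their own products, and the documents give no basis for an excess. The other is that the trial's main result is compromised: the primary purchasing data come from Virtual Visits 2-5 and are complete before hand-over. The discretionary withdrawal list is outside the point, since CO is measured at Lab Visit 2, conduct can be observed, and other hospitalization is expressly left to self-report and review.

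**What to change.** At In-Person Lab Visit 2, before hand-over:
- Give the existing Health Changes Questionnaire with all recall periods set to since Virtual Visit 1, plus the phone screener's pregnancy/breastfeeding question. Have staff read the answers before releasing products.
- Withhold products and withdraw for any of the five events. Refer other new serious conditions, breastfeeding or other hospitalization to the PI and medical monitor under the existing discretionary rule, with no automatic withdrawal.

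In the text, name Lab Visit 2 as an assessment point under Identifying Adverse Events and in the pregnancy item. Set the Virtual Visit 6 recall to since In-Person Lab Visit 2, so that the two look-backs join.

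The cost is a few minutes per participant at an existing visit and a short amendment. A few withdrawals may follow. Each loses that participant's field-assessment data, which feed secondary and exploratory outcomes, and counts against the 64 completers. The protocol recruits up to 100 to reach 64 but does not say how much of the difference is meant for ineligibility at screening, so it should not be read as spare capacity for these withdrawals.

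Two limits remain. Self-report will not find an unrecognized pregnancy, and the age of the urine test at hand-over is unchanged. A truthful yes still costs the participant the $50 bonus.

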Research staff will conduct in-depth interviews with the participants to assess the following constructions: 1) decision-making during the ETM task; 2) use of alternative products during the field assessment; 3) product risk perceptions and; 4) opinions regarding possible tobacco control policies.

In-Person Lab Visit 3

In-Person Lab Visit 3 will be completed up to 48 hours after completing Virtual Visit 6. Participants will complete the COVID screener within 24 hours of their Lab visit via email or phone. Research staff will wear personal protective equipment during the visit including face masks and gloves. The participants will be required to wear facemasks when interacting with the staff. Temperature checks will be conducted immediately upon arrival using a thermal heat scanner. Participants will bring a first void urine sample, which will be banked for future biomarker analysis (e.g., total nicotine equivalents) and all of their used/unused products.

Participants will provide CO readings at least 6-feet away from other people, including the research staff, while they have their masks off. Participants will complete a second iteration of discrete choice task 1. Data from the two choice tasks will be compared within participants to see whether product use affected preferences.

All participants will be emailed a cessation manual and local smoking cessation resources.

Product adherence

To verify self-reported tobacco use, all used and unused products will be collected and counted at In-Person Lab Visit 3. Discrepancies between consumption stated on the TLFB versus consumption based on the products returned will be addressed. Non-adherence (i.e., using products not purchased from the ETM) will be assessed via the TLFB and qualitative interview with the importance of honest self-reporting emphasized. If participants report not using combusted tobacco, then CO readings < 6 ppm will verify their self-report.

Compensation

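### Minor, cheap improvement: the Health Changes Questionnaire is given only at Virtual Visit 6, so no general symptom question is scheduled for the 0 to 48 hours before products come back at In-Person Lab Visit 3

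*Combined protocol and SAP*

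**What the plan says.** The section Identifying Adverse Events gives the schedule: "adverse events will be assessed at Virtual Visit 6 and carbon monoxide levels from In-Person Lab Visit 3". It names the main source, "Adverse events will typically be identified during the administration of the Health Changes Questionnaire", and a second one, "Other adverse events may be identified by spontaneous reports from the participant". The questionnaire has three questions, on health changes, medical care received and medication changes. All look backwards. The first asks "Have you had any negative changes in your physical or mental health since your last virtual visit", the second uses the same reference point, and the third asks "Have you had any changes in medication since your last visit".

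The visit descriptions list this form once, among the self-administered surveys at Virtual Visit 6. That visit falls seven days after In-Person Lab Visit 2, where products are handed out with an instruction to use only those products for seven days. Then "In-Person Lab Visit 3 will be completed up to 48 hours after completing Virtual Visit 6", and under Product adherence "all used and unused products will be collected and counted at In-Person Lab Visit 3". The procedures listed for Lab Visit 3 are the COVID screener, a temperature check, the urine sample, product return, CO and the second discrete choice task. The Health Changes Questionnaire is not among them.

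The withdrawal rules that close the safety section add two routes. A pregnancy indicated at Virtual Visit 6 or Lab Visit 3 leads to withdrawal and follow-up on an Adverse Event Form. Self-reported hospitalization or debilitation is reviewed by the principal investigator and the medical monitor.

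**The concern.** The last scheduled symptom question comes before the products are returned, although completers are seen in person within the following 48 hours. The protocol treats that last contact as part of adverse-event assessment, since it reads CO there and acts on a pregnancy indicated there. It does not schedule the three general health questions.

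CO does not replace those questions. It cannot detect most of the effects listed under Potential risks of participation for vaping devices and nicotine gum, such as throat irritation, nausea, dizziness or palpitations, nor changes in mood. Lab Visit 3 also lists no new timeline follow-back interview, so neither product use nor symptoms after Virtual Visit 6 are asked about as a scheduled item.

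At stake is a short stretch of symptom ascertainment at the end of participation. Three things could fall in it: use of leftover products, return to the usual brand, and symptoms that begin only after Virtual Visit 6.

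**Working it through.** The plan gives no figure to reproduce. The check is to line up the visits and work out the intervals.

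**Inputs**
- Lab Visit 2 to Virtual Visit 6: 7 days × 24 = 168 h (Virtual Visit 6), taken as exact.
- a = hours from Virtual Visit 5 to Lab Visit 2: 0 to 48 (In-Person Lab Visit 2).
- d = hours from Virtual Visit 6 to Lab Visit 3: 0 to 48 (In-Person Lab Visit 3).

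**Step 1: what the questionnaire covers now**
- Questions 1 and 2 look back to Virtual Visit 5: 168 + a = 168 to 216 h.
- Question 3 looks back to the last visit, read here as Lab Visit 2: 168 h. If it were read as the last virtual visit, the span would be 168 + a.
- On either reading, all 168 h of instructed use are covered.

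**Step 2: what falls after it**
- Products can be held for 168 + d = 168 to 216 h.
- The part after the questionnaire is d, and its share of possession time is d / (168 + d).

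| d (h) | Possession (h) | Share after the questionnaire |
|---|---|---|
| 0 (visits coincide) | 168 | 0/168 = 0% |
| 24 | 192 | 24/192 = 12.5% |
| 48 (latest allowed) | 216 | 48/216 = 22.2% |

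These shares are ceilings on time in possession and apply only to people who still hold products. Under Virtual Visits 2-5, participants may buy few products or none, and balances are set at about seven days of cigarette spending, so some will have nothing left.

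**Step 3: with the three questions repeated at Lab Visit 3**
- At that point the last virtual visit and the last visit are both Virtual Visit 6, so each question looks back d = 0 to 48 h.
- Combined span, Questions 1 and 2: 168 + a + d = 168 to 264 h.
- Combined span, Question 3: 168 + d = 168 to 216 h, equal to possession time.
- Possession time without a scheduled question falls from d (0 to 48 h) to 0 h.

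The documents give neither the actual visit lag nor an event rate, so no expected number of missed events can be calculated.

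**The case against.** The strongest case on the other side is that placing the one scheduled health questionnaire at the end of instructed use is a coherent choice. It covers the period in which participants are told to use the products. Participants are established daily smokers who have tried vaping, and those with serious medical or psychiatric conditions are excluded. The documents identify no hazard particular to the hours after Virtual Visit 6, and nothing in them requires symptom questioning up to product return. The effects listed for returning to the usual brand are mild and transient, and a repeat at Lab Visit 3 would not capture a later return. Staff also see the participant in person, so a volunteered report has an immediate route. All of this stands, and it is why the point is an improvement and not an error.

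A reader might go further and infer that the protocol has no source other than CO and spontaneous reports for this interval. The documents do not support that, because the withdrawal rules also act on pregnancy indicated at Lab Visit 3 and on self-reported hospitalization or debilitation. Both depend on the participant reporting, and neither is a general symptom question.

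Two other contacts might pick something up. "Participants will complete the COVID screener within 24 hours of their Lab visit via email or phone", and that screener could overlap with symptoms such as cough. The product count could reveal use of leftovers as a discrepancy with the timeline follow-back. The screener's content is not given, and neither contact is linked to adverse-event capture, so neither closes the gap.

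**Conclusion.** The point holds as a minor, low-cost improvement. For 0 to 48 hours between Virtual Visit 6 and product return, no general symptom question is scheduled. CO is measured at Lab Visit 3, and the rest depends on what participants report unprompted, including under the pregnancy and hospitalization rules.

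The 22% maximum should not be read as the share of exposure that goes unmonitored. It assumes the latest permitted visit and a participant with leftover products, and the range starts at 0%. Nor do the documents support the inference that adverse events from the field assessment's instructed use go unasked. That week is covered at Virtual Visit 6.

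Adverse events are not among the listed outcomes, and the purchasing results, sample size and analysis are unaffected. The conclusion rests on two assumptions: that Virtual Visit 6 falls exactly seven days after Lab Visit 2, and that the visit lists are complete as printed.

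**What to change.** Add the existing three-question Health Changes Questionnaire to the procedures for In-Person Lab Visit 3, when products are returned. Amend Identifying Adverse Events to state that adverse events are assessed at both Virtual Visit 6 and Lab Visit 3, with CO measured at Lab Visit 3. Virtual Visit 6 stays as it is, and the questions need no rewording.

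The cost is a few minutes per participant at a visit that already takes place, with existing staff and an existing form, one added sentence in the visit description and one amended sentence in the safety section. The downside is slightly more adverse-event paperwork. If the two visits fall on the same day, the repeat adds little. It does not reach participants who miss Lab Visit 3, or effects that begin after it.

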Discrete choice task 1: The Sawtooth Lighthouse Studio platform will host a discrete choice task (See DCE Questionnaire). First, participants will rate the appeal of cigarettes and e-cigarettes characteristics, which helps familiarize them with the product features that will be manipulated in the choice task. Next, the choice task will begin, and they will make several choices between a cigarette option and an e-cigarette option responding to a prompt that asks which they would rather use exclusively for the next week. Each cigarette vs e-cigarette trial will present different combinations of cigarette nicotine content, e-liquid nicotine content, and e-liquid flavor. Finally, the participant will complete follow-up questions about which characteristics most informed their choices. The data from this task will reveal how participants prioritize and make tradeoffs between product type, nicotine content, and flavor when forming preferences.

After completing the discrete choice procedure, participants will also be given the opportunity to sample the low and normal nicotine Spectrum investigational cigarettes available during the ETM (up to 4 puffs each). Other products will also be available on the ETM, but will not be available for sampling. These include: fruit, dessert, menthol, and tobacco flavored e-liquids; and mint, fruit and cinnamon flavored nicotine gum.

Virtual Visits 2-5

Participants will complete Virtual Visit 2 between 1 and 21 days after completing In-Person Lab Visit 1. Virtual Visits 2-5 will ideally be conducted four days in a row to reduce online task fatigue. However, visits may be scheduled up to 7 days apart.

The following assessment will be administered as an interview and entered into REDCap by the interviewer:

1. Timeline Follow Back (TLFB) Questionnaire, which will assess tobacco and nicotine product use since their last virtual visit.

Participants will complete the ETM task on the computer. If the participant needs assistance with navigating the online marketplace the research staff may screen share and allow the participant to verbally select the items that they would like to purchase. The products available on the ETM include:

- Spectrum cigarettes
- Fruit, dessert, mint and tobacco e-liquids (e.g., Vaporesso Xross Mini)
- Mint, fruit, and cinnamon nicotine gum (e.g., Nicorette).

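### The only scheduled adverse-event questionnaire looks back no further than Virtual Visit 5 and uses two different anchors, so events between consent and Virtual Visit 5 are not actively asked about

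*Combined protocol and SAP*

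**What the plan says.** The section on identifying adverse events frames assessment as taking place during study participation and then fixes its timing: "adverse events will be assessed at Virtual Visit 6 and carbon monoxide levels from In-Person Lab Visit 3". It names the main instrument: "Adverse events will typically be identified during the administration of the Health Changes Questionnaire". Spontaneous reports are the other route it names.

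The instrument has three trigger questions:

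- Question 1: "Have you had any negative changes in your physical or mental health since your last virtual visit".
- Question 2: "Since your last virtual visit, have you received any form of medical care".
- Question 3: "Have you had any changes in medication since your last visit".

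The visit descriptions list this questionnaire under Virtual Visit 6 only.

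The same section lists events that lead to immediate withdrawal. For suicide attempt the rule reads: "A participant will be withdrawn if they attempt suicide at any time during participation in the study". The rule for psychiatric hospitalization has the same scope. The cardiovascular and DVT/PE items state no period, and the pregnancy item is tied to Virtual Visit 6 or In-Person Lab Visit 3.

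**The concern.** A questionnaire given once, with its recall tied to the preceding visit, can ask only about the interval since that visit. Here that interval is the last stretch of the study. A participant who received medical care, was hospitalized or changed medication between consent and Virtual Visit 5 could truthfully answer no to all three questions, because the wording places those events outside the period asked about.

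Two things are at stake. The adverse-event record would be less complete for the earlier part of participation than for the later part, and the plan does not acknowledge this. The period covered by the questions also differs from the period covered by two of the withdrawal rules in the same section. The third question adds an ambiguity: it drops the word for a virtual visit, so one form carries two look-back periods.

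**Working it through.** The plan states no figure for this period, so there is none to reproduce. The check compares the recall wording with the visit schedule and adds up the visit windows.

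**Is there another scheduled health question before Virtual Visit 6?**

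| Contact | Health-related content listed |
|---|---|
| Virtual Visit 1 | Brief medical history and concomitant medications, at screening |
| Lab Visit 1 | COVID screener, temperature, CO, urine pregnancy test where applicable, withdrawal and craving scales |
| Virtual Visits 2-5 | Timeline Follow Back on tobacco and nicotine use, then the marketplace task; no health question |
| Lab Visit 2 | COVID screener, temperature, CO |
| Virtual Visit 6 | Health Changes Questionnaire |

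After the screening forms at Virtual Visit 1, no listed item before Virtual Visit 6 asks about general health, psychiatric events, medical care or medication changes.

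**Inputs, from the visit descriptions**

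- Lab Visit 1 to Virtual Visit 2: 1 to 21 days.
- Virtual Visit 2 to Virtual Visit 5: ideally four consecutive days, so 3 days. Visits may be up to 7 days apart. Taken between consecutive visits, that is 3 × 7 = 21 days.
- Virtual Visit 5 to Lab Visit 2: 0 to 2 days.
- Lab Visit 2 to Virtual Visit 6: 7 days.

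**Look-back at Virtual Visit 6**

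- Questions 1 and 2, back to Virtual Visit 5: 0 + 7 = 7 to 2 + 7 = 9 days.
- Question 3, read literally back to Lab Visit 2: 7 days.

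**Period not asked about, Lab Visit 1 to Virtual Visit 5**

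- Shortest: 1 + 3 = 4 days.
- Longest: 21 + 21 = 42 days.
- With the ideal four-day run: 1 + 3 = 4 to 21 + 3 = 24 days.
- If the 7-day limit covers the whole run of Virtual Visits 2-5: at most 21 + 7 = 28 days.

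**Share of calendar time from Lab Visit 1 to Virtual Visit 6**

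- Lowest: 4 / (4 + 9) = 31%.
- Highest: 42 / (42 + 7) = 86%. Under the 28-day reading: 28 / (28 + 7) = 80%.

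These day counts are minimums for the whole of participation. Consent is signed at Virtual Visit 1, and the interval from there to Lab Visit 1 is also outside the look-back. The plan gives no window for that interval, so it is not counted.

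**Product exposure in each period**

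- Before Virtual Visit 5: optional sampling at Lab Visit 1 of two investigational cigarettes, up to 4 puffs each.
- After Virtual Visit 5: products dispensed at Lab Visit 2 for seven days of use. All of this falls inside the look-back of all three questions, even on the literal reading of Question 3.

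**The case against.** The strongest reply is that the recall window fits the intervention. Take-home products are first handed over at Lab Visit 2, so a look-back to Virtual Visit 5 captures the whole dispensed-product period. Earlier exposure is a few puffs in people who already smoke at least 5 cigarettes a day. Adverse events are not among the primary, secondary or exploratory outcomes. All of this stands, and it keeps the point small. It does not explain why the two anchors differ, or why the questions cover less than the participation period to which two of the withdrawal rules apply.

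A reader might be tempted to infer more than the documents support:

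- **That the trial misses every event before Virtual Visit 5.** This is true of the form only. The plan also accepts spontaneous reports, and its discretionary withdrawal list relies on participants reporting hospitalization themselves. Staff meet participants at each of Virtual Visits 2-5 and at Lab Visit 2, so there are occasions for a report, though no scheduled prompt.
- **That the withdrawal rules cannot be applied to the earlier period.** A withdrawal rule says what follows once an event is known; the questionnaire is one way of learning of it. The rules still apply to any event that becomes known.
- **That all withdrawal rules cover any time in the study.** Only the suicide-attempt and psychiatric-hospitalization items say so.
- **That 31% to 86% of the safety information is lost.** Those are shares of calendar time. For the seven days of dispensed-product use, the uncovered share is zero. The upper figure also needs every window before Virtual Visit 5 at its maximum and no gap between Virtual Visit 5 and Lab Visit 2.

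**Conclusion.** The point holds as one about ascertainment. Between consent and Virtual Visit 5, adverse events are not actively asked about. Counted from Lab Visit 1, that period is at least 4 to 42 days, assuming the 7-day limit runs between consecutive visits; the maximum is 28 days if it covers the whole run of four visits. The questions cover the 7 to 9 days before Virtual Visit 6, or 7 days for Question 3 read literally.

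The consequence is a less complete adverse-event record for a period of minimal study-product exposure, and a mismatch between the questions' look-back and the participation-wide scope of two withdrawal rules. The primary analysis and the power calculation are unaffected. This is a modest point, worth acting on because the remedy is cheap.

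**What to change.** Reconcile the look-back in Questions 1-3 with the period that the section's own rules cover, and state that period in the section. Use one explicit anchor for all three questions that matches participation. For example, each could begin: *Since you signed the consent form at Virtual Visit 1 on [date], ...* Anchoring at Lab Visit 1 would leave the interval from consent to Lab Visit 1 uncovered.

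The cost is rewording three questions on an existing form, with no added visit or procedure. The downside is longer recall: 4 + 7 = 11 to 42 + 9 = 51 days from Lab Visit 1, plus the unstated interval from Virtual Visit 1, in place of 7 to 9 days.

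The limit of the change should be understood. A question asked at Virtual Visit 6 completes the record after the event; it does not detect events before products are dispensed at Lab Visit 2.
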